2018). This project therefore seeks to: 1) undertake a hydrotherapy intervention in boys and adolescents with DMD and 2) conduct qualitative Patient and Parent interviews to understand the potential barriers and hidden benefits to hydrotherapy not captured in our outcome measures.

Research Objective:

It is hypothesised that undertaking hydrotherapy will result in a beneficial change in the primary outcomes of QoL, bodily pain, and body composition, and secondary outcomes of physical function (e.g. Range of motion strength, and upper limb function), where possible.

The **aim** of this study is to determine whether hydrotherapy can mitigate some of the weight gain, bodily pain, lower QoL and functional impairments associated with progression of DMD in young males.

Potential outcomes include:

- 1) improvements in all outcome measures as a result of undertaking hydrotherapy (increased lean muscle mass, reduced body fat; improved functional measures (e.g. strength), activities of daily living, ROM; improved quality of life, and lowered bodily pain).
- 2) no change in outcome measures following hydrotherapy but a relative slowing of the decline observed during the “control period”.
- 3) outcome measures continue to deteriorate at the same rate as the control period.
- 4) a worsening of outcome measures compared to the control period.

Objectives and Specific Aims:

Outcomes

This project will yield 4 experimental journal articles.

1. The impact of hydrotherapy on body composition and muscle mass in boys with DMD
2. The impact of hydrotherapy on QoL and bodily pain in boys with DMD
3. The impact of hydrotherapy on muscle function and activities of daily living in boys with DMD
4. Practical considerations and barriers to hydrotherapy in young people with DMD, a qualitative review of interviews with parents, carers and those with DMD.

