While natural history studies indicate an overall negative trend in the abilities of patients with DMD, there is great variability in age and speed of deterioration (Muntoni et al., 2019). As such it is difficult to find matched controls for a short randomised intervention study. Instead, due to the progressive nature of DMD and the inherent variance within a mixed age, and ability population (e.g. upper limb & respiratory function, genetic variation etc.(Ricotti et al., 2019)), the participants will act as their own controls. This single-arm, non-crossover design where the participant acts as his own control, although not as robust as randomized control exercise trials, is advocated for longitudinal interventions in populations such as the present one (Hecksteden et al., 2018). Indeed, this self-controlled approach offers some of the benefits of prospective controlled trials, allows for multiple treatments within the same participants, and eliminates some of the covariates of group comparisons which are inherent in dual arm training studies (Vohra et al., 2015). Specifically with treatments such as hydrotherapy, the process of randomisation leads to patient and parent disengagement due to not getting to undertake a treatment (Hind et al., 2017). This self-controlled study avoids the downsides of randomisation for the participants and is consistent with previous exercise training studies both in non-clinical (Narici et al., 1989), and in our own training studies in muscular dystrophy (Bostock et al., 2019).

Research Design

The **aim** of this project is to undertake 12-weeks of hydrotherapy in boys and adolescents with DMD, and monitor the impact on body composition, bodily pain, QoL and physical function. The project is broken down into 3 key stages:

Pre-experimental stage: during this stage we will secure ethical approval, and recruit participants. This stage will last ~6 months due to the length of time it takes to secure NHS ethical approval.

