Experimental stage: the participants will complete the experimental protocol described below in detail. Briefly, participants will complete TWO 12-week periods. The first will be an observation (control) period to use as a reference point for the second period, which will involve 12-weeks of hydrotherapy. *Figure 1* attached describes the testing sessions; these will be completed at 3 time points, the first before the control period, the second after the control period, and the third after the hydrotherapy period. The experimental stage will last 28-months due to the staggered recruitment and testing of participants.

Post experimental stage: this stage will involve the analysis of data and production of academic papers for submission within international journals. This stage will be scheduled for 4-months but will continue until the data has been published. Although the cost of a dissemination event is not formally included within this bid; as researchers and clinicians we regularly update physiotherapists, carers, clinicians and those with DMD through dissemination events. We plan to present our findings at events hosted through the

Northwest Neuromuscular Network, The Neuromuscular Centre outreach and dissemination days, and through the hospice website.

Experimental stage protocol

Participants will complete two 12-week periods, including an initial control period (CTRL), where they will undertake their habitual physical activity behaviour. This will be followed by 12-weeks of hydrotherapy, where participants will complete up to 60 mins of hydrotherapy once a week. During these CTRL and hydrotherapy periods, diet and physical activity will be monitored to identify any lifestyle covariates that could contribute to their body composition and physical and mental wellbeing. Pre and Post CTRL, and Post hydrotherapy, participant outcome measures will be re-assessed.

Consent: consent will be obtained from patients 16 years and older or parents / guardians of children younger than 16 years of age, either face to face or via a pre-arranged video link with a member of the research team who is signed off the delegation log as being able to take consent.

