Within their 24 sessions of hydrotherapy, Fransen et al (2007) report effect sizes above that of control of 4.0, with no change in their control group. If we make the assumption that within our 12 session intervention we are likely to see half of the improvement in QoL, we shall base our power analysis of an effect size of 2 compared to that of controls. With the following values, within participant *apriori* power calculation performed using G*Power (Version 3.1.7, University of Kiel, Germany) suggests a total group number of n = 8 (α err prob=0.05, Power 0.95). We feel this is too conservative given that we also need to a) account for drop-out of participants and b) fulfil the criteria for parametricity in a clinical condition that has a wide variance (children and adults with DMD ranging from 6-25 yrs are very varied in the presentation of physical function). Therefore, given the aforementioned considerations and as this is a novel intervention in terms of research outcomes and will serve as a primary point of reference for subsequent hydrotherapy studies within DMD, we will recruit 44 participants in total.(See also *table 1*, summarising published hydrotherapy trials in similar medical conditions)

Participants will be recruited through the respective neuromuscular clinic and through Derian House hospice.

Inclusion criteria

- Established diagnosis of Duchenne Muscular Dystrophy (either by genetics or muscle biopsy)
- Between 6 and 25 years of age
- On stable dose of steroids or not on steroids

Exclusion criteria

- Younger than 6 years, older than 25 years
- Recent change in steroid dose, less than 3 months prior
- Undertaking formal hydrotherapy supervised by physiotherapist on a regular basis (weekly or more frequent)

Body composition

Fat mass, body fat percentage and fat free mass will be measured using bioelectrical impedance (BIA). Although more stringent measures of body composition exist such as dual-energy X-ray absorptiometry (DEXA), BIA has been validated in DMD and is accurate enough to measure longitudinal changes in body composition and muscle mass in this population (Mok et al., 2010; Kuru et al., 2019).

Physical function

Established physical function assessments for individuals with neuromuscular conditions will be completed. These will include the North-Star and Performance of the Upper Limb assessment (Mayhew et al., 2013); and an assessment of activities of daily living (Wu et al., 2011).

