The exercises, intensity and specific hydrotherapy session plan will be derived from consultation between the participants, and clinical physiotherapist. Due to the variance within the presentation of the condition and the inclusive age range within the study, we will take what we consider as an externally valid approach to exercise prescription. We will record heart rate during a sample of the participants' hydrotherapy sessions, which will be included as a co-variate for subsequent analysis.

Hydrotherapy will be conducted at Derian House Children's Hospice (Chorley, UK), and may include weight-bearing activities such as standing and gait practice, assisted and resisted limb exercises. Core and trunk work including swimming.

Please find attached

Figure 1-experimental overview

Figure 2-GANTT chart

Figure 3- proposed experimental workflow

Table 1 -current research in hydrotherapy

Data Analysis:

All participants will be assessed using a repeated measures design. Given the broad heterogeneity of DMD participants recruited there is no meaningful benefit of intergroup comparisons between those participants who can complete 30-60 mins of active hydrotherapy, compared to those who can perform arm only, or passive hydrotherapy. Experimentally it is not of interest if one group changes more than another, it is of interest if there is a change within the individuals themselves. We have recently completed a resistance training protocol in adults with MD and adopted a similar approach (Bostock et al., 2019).

Participants will be assessed against previous time points (Pre-CTRL vs Post-CTRL vs Post hydrotherapy) using repeated measures Anova (where outcomes are parametric) or Friedman's (where parametric assumptions are violated). Tests of association will be used to compare relative hydrotherapy intensity with changes from PRE to Post hydrotherapy.

Adverse Events:

All adverse events will be reported to the Chief Investigator and study Sponsor. Depending on the nature of the event the reporting procedures below will be followed. Any questions concerning adverse event reporting will be directed to the Chief Investigator in the first instance.

Adverse Events

If an incident needs acute attention, a member of the research team will follow local emergency procedures.

These will be recorded using the Adverse Event Reporting form, discussed with CI and paediatricians/ physiotherapist of team and escalated to the study Sponsor.

Serious Adverse Events

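### The three-visit ANOVA or Friedman test does not compare change during hydrotherapy with change during the control period, so a steady trend alone can make it significant

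*Protocol*

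**What the plan says.** Research Design gives the control period its role: "The first will be an observation (control) period to use as a reference point for the second period".

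Research Objective lists four possible results:

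- Result 1 is absolute improvement: "improvements in all outcome measures as a result of undertaking hydrotherapy".
- Result 2 is benefit without improvement: "no change in outcome measures following hydrotherapy but a relative slowing of the decline observed", judged against the first 12 weeks.
- Result 3 amounts to no effect of hydrotherapy: "outcome measures continue to deteriorate at the same rate as the control period".
- Result 4 is decline that becomes faster once hydrotherapy starts: "a worsening of outcome measures compared to the control period".

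Results 2 to 4 are defined by comparing the two periods. Participants and power calculation also sets its target against control: "we shall base our power analysis of an effect size of 2 compared to that of controls".

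Data Analysis then names the test: "Participants will be assessed against previous time points (Pre-CTRL vs Post-CTRL vs Post hydrotherapy) using repeated measures Anova" for parametric outcomes, and Friedman's test otherwise. The only other analysis named relates session intensity to change. No comparison of the two period changes is named.

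**The concern.** The null hypothesis of the named test is that the three visits have equal levels. The study's null hypothesis is that the two periods have equal change. The two coincide only when the outcome has no trend, and the protocol expects a progressive condition.

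Under the protocol's own result 3, the same decline with no hydrotherapy effect, the visit means differ and the test can reject for a reason unrelated to treatment. Pairwise visit comparisons do not repair this:

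- Post-CTRL versus Post-hydrotherapy does address result 1, absolute improvement. It carries the same background trend, however, and cannot separate slower, equal and faster decline.
- A significant fall in the control period with none during hydrotherapy is not a test of the difference between the two falls.

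The control period would then be collected but not used as a comparator. Slowing of decline, which the protocol counts as a benefit, would go untested.

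**Working it through.** **The plan's own figure.** Participants and power calculation gives n = 8 for an effect of 2, alpha 0.05 and power 0.95. A two-sided paired t-test with standardised effect 2 needs n = 6 (power 0.97), so 8 is reproduced only roughly, and only if 2 is a standardised effect. The present point does not depend on that figure.

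**Inputs.** From the protocol: three visits, two 12-week periods, n = 44, alpha 0.05 (taken as two-sided). Assumed, because the protocol does not give them: outcome SD 1, equal correlation ρ = 0.8 between visits (range 0.6 to 0.9), and a decline d of 0.1, 0.2 or 0.3 SD in the control period.

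**ANOVA.** The F test has 2 and 86 df and noncentrality λ = n Σ(μⱼ − μ̄)² / (1 − ρ).

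| Hydrotherapy period | Visit means | Σ(μⱼ − μ̄)² | λ at ρ = 0.8 | Rejection at d = 0.1 / 0.2 / 0.3 |
|---|---|---|---|---|
| Same decline (no effect) | 0, −d, −2d | 2d² | 4.4 / 17.6 / 39.6 | 44 / 97 / 100% |
| Decline halted | 0, −d, −d | (2/3)d² | 1.47 / 5.87 / 13.2 | 17 / 56 / 90% |
| Decline doubled | 0, −d, −3d | (14/3)d² | 10.3 / 41.1 / 92.4 | 81 / 100 / 100% |

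Rejection is least frequent when hydrotherapy stops the decline and most frequent when decline accelerates.

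**Other results with no hydrotherapy effect**, at d = 0.1 / 0.2 / 0.3 and ρ = 0.8 unless stated:

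- Friedman (simulated): 33 / 89 / 100%.
- Post-CTRL versus Post-hydrotherapy, paired t: 18 / 54 / 87%.
- Significant fall in the control period and none in the hydrotherapy period (simulated): about 17 / 33 / 13%.
- ANOVA over ρ = 0.6 to 0.9: 24–75%, 75–100%, 98–100%.
- Slopes varying between patients with SD 0.1 to 0.3 (simulated): ANOVA 31–42%, 84–95%, 99–100%; Friedman 22–32%, 67–86%, 96–100%. This matters because the design justification says "there is great variability in age and speed of deterioration".
- Smaller trends, ANOVA: 5% at d = 0, 6% at 0.02, 14% at 0.05.

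Scaling the decline in SDs of a 12-week change removes ρ (λ = 4nd²). The no-effect ANOVA rate is then 20 / 64 / 95% at 0.1 / 0.2 / 0.3.

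**The matching contrast.** Let D = (Post-hydro − Post-CTRL) − (Post-CTRL − Pre-CTRL).

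- With the same decline in both periods, E(D) = −d − (−d) = 0. Simulated rejection stays at about 5% for every steady trend tried.
- Var(D) = 6(1 − ρ), against 2(1 − ρ) for a simple change: three times the variance.
- At ρ = 0.8, SD(D) = √1.2 = 1.095. The 95% CI half-width is 2.017 × 1.095 / √44 = 0.33 SD.
- If decline is halted, E(D) = d, and the noncentral t with 43 df gives 9 / 22 / 43% power. At d = 0.2 the range over ρ = 0.6 to 0.9 is 13–39%.
- 80% power needs a standardised effect of 0.432. That is 0.432 × 1.095 = 0.47 SD for D, against 0.432 × √0.4 = 0.27 SD for a simple change.
- If the effect of 2 is read as 2 QoL points (an assumption), with the protocol's SDs of 5.9 and 8.5, D has 52% and 29% power. A simple change has 94% and 67%.

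**The case against.** **The ANOVA model already contains the contrast.** With three equally spaced visits its quadratic contrast is D, and follow-up contrasts are often left to the SAP, which is not at hand. This is true of the model, but the protocol names the comparison of visits as the analysis, and Friedman's test has no such contrast.

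**The rejections are not false claims of benefit.** The hypothesis is directional, and under steady decline a significant result shows falling means. Post-CTRL versus Post-hydrotherapy would be significant in the favourable direction in only about 0.14% of no-effect trials at d = 0.1. This stands: the percentages above measure a time effect that could be credited to hydrotherapy, not false benefit. But λ depends on d², so a steady favourable trend, such as growth in lean mass or a practice effect, gives the same rejection rates in the favourable direction. For declining outcomes, slowing remains undetected.

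**The trend is undocumented.** The protocol describes decline in abilities, which are secondary outcomes, and gives no 12-week size for QoL, pain or body composition. This also stands and limits the figures. It does not remove the mismatch between question and test.

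**The power section is weak support.** Its target comes from an osteoarthritis trial whose control group did not change, where D and a simple change have the same expected value. That is fair; the case rests mainly on Research Objective and Research Design.

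**D has low power.** It does, and lower still after drop-out: with 32 completers (illustrative), power for a full halt is 8 / 17 / 32%. That is a reason to state the precision openly and to report the simple change beside D.

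**Conclusion.** The concern holds and should be settled before the analysis is fixed. The test named in Data Analysis does not answer the question set in Research Objective and Research Design. A significant omnibus result cannot by itself be attributed to hydrotherapy, and slowing of decline is never tested.

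The size depends on assumed trends and correlations. With 44 completers and correlation 0.8, the ANOVA's rejection rate with no hydrotherapy effect is 14% at a decline of 0.05 SD per period, 44% at 0.1 SD and 97% at 0.2 SD. It stays at 5% when there is no trend. The mismatch itself needs no assumed number.

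**What to change.** In Data Analysis:

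- Make the main test the within-participant contrast D, reported with a 95% CI. Use a one-sample t-test, or a signed-rank test on D where it is clearly non-normal.
- Report the Post-CTRL to Post-hydrotherapy change with its CI as supportive, for result 1.
- Keep the three-visit ANOVA or Friedman test as descriptive.
- If the intensity association is kept, relate intensity to D.

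In Participants and power calculation, restate the precision for D and for the number of completers expected.

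No visits or data are added. The cost is precision: under equal visit correlations D has three times the variance of a simple change, so a null result would be inconclusive and the CI should carry the conclusion. D also assumes that the control-period rate would otherwise have continued, and the protocol should say so.

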If consent is taking place face to face, a suitable time will be arranged between a member of the research team and the family. Consent can take place during the patient's usual Neuromuscular clinic or at an independent appointment at the Clinical Research Facility (CRF). This is also a good opportunity for the young person to familiarise themselves with the CRF.

If consent is taking place via a pre-arranged video link, a suitable time will be arranged between patient/parents/guardians and a member of the research team. Microsoft Teams, Attend Anywhere or Zoom are acceptable platforms that can be used depending on individual Trust guidelines. A copy of the PIS and the appropriate consent form (with all details completed by Research Team as needed) will be posted to the family with a pre-paid return envelope.

During the consent appointment, either face to face or via video link:

1. A member of the research team will confirm they have received the PIS, have read it and have understood it.
2. Patient/ Parents / guardians will be asked if they have any questions.
3. Questions will be answered until they are content.
4. The research team member taking consent will re-confirm the fact that the child can be withdrawn at any time without giving any reasons and that this will not affect the physiotherapy treatment the child receives.
5. The patient/parents/guardians will then be given the consent forms. They will be asked to read every statement, initial each box, and sign and date at the end of the form.
6. The research team member taking consent will then sign and date the form. If appointment is completed via video link, the wet ink copy is posted back to the research team to sign and date and note that the form was completed by parents during the video link.
7. The wet ink copy will be kept by the research team member.

8. A copy of the signed consent will be given to the patient/ parents / guardian to keep for their own records. If via video link, this copy will be posted to parents or given when the family attend for their initial assessment.

Participants and power calculation

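### Repeated-measures ANOVA and Friedman's test drop anyone missing one of three visits; a mixed model (Skillings-Mack for ranks) would keep partial records cheaply, mainly when loss comes after Post-CTRL

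*Protocol*

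**What the plan says.** Data Analysis opens with "All participants will be assessed using a repeated measures design". It then compares the three assessments "using repeated measures Anova (where outcomes are parametric", and by Friedman's test "where parametric assumptions are violated". No other method is named for the visit comparison.

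Three other sections bear on this choice:

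- **Research Design, Experimental stage:** of the two 12-week periods, "The first will be an observation (control) period to use as a reference point for the second period".
- **Research Objective:** the possible results are framed against that period, for example "a relative slowing of the decline observed during the" control period, or "outcome measures continue to deteriorate at the same rate as the control period".
- **Participants and power calculation:** the target is raised to 44, partly to "account for drop-out of participants". No drop-out rate or mechanism is given. Under Consent, families are told that "the child can be withdrawn at any time without giving any reasons".

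**The concern.** Both named tests, in standard form, need all three visits from each participant. Someone who completes the control period and leaves during hydrotherapy has supplied a full control-period change, yet it is discarded. In a single-arm trial whose only reference is the control period, the comparator is then estimated from completers alone.

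Recruiting more participants restores precision but does not remove selection. The disease is progressive and, by the protocol's own account, its speed varies widely, so loss related to decline is plausible, though the protocol does not say it will occur. Two things are at stake: precision if loss is random, and bias and false-positive rates if loss follows outcomes already observed.

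**Working it through.** The protocol has no figure of its own on missing visits to reproduce.

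**Inputs.** From the protocol: n = 44 and three visits. Assumed: higher scores are better; y = intercept + slope × visit + noise, with intercept variance 0.8, noise variance 0.2 and slope SD 0.15 (visit correlation about 0.8); decline of 0.2 SD per period; no hydrotherapy effect; 20% loss after Post-CTRL, so 0.8 × 44 = 35.2 expected completers. Where loss is not random, the log-odds are 0.5, 1 or 2 per SD. Figures separated by slashes follow that order unless stated.

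**Step 1: precision under random loss.** Variance of a one-period change = 2 × 0.2 + 0.15² = 0.4225. Variance of the difference of changes (y3 − 2·y2 + y1) = 0.2 × (1 + 4 + 1) = 1.2; the slope cancels. With visits coded 0, 1, 2, the variance of y3 given y1 and y2 is 1.09 − 0.7499 = 0.3401. A likelihood analysis uses all 44 for the part predicted by the first two visits and the 35.2 completers for the rest.

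| Quantity | Completers' SE | Mixed-model SE | Excess |
|---|---|---|---|
| Control-period change | √(0.4225/35.2) = 0.110 | √(0.4225/44) = 0.098 | 12% |
| Hydrotherapy-period change | √(0.4225/35.2) = 0.110 | √(0.0824/44 + 0.3401/35.2) = 0.107 | 2% |
| Difference | √(1.2/35.2) = 0.185 | √(0.8599/44 + 0.3401/35.2) = 0.171 | 8% |

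In the same order, the excess is 5/1/4% at 10% loss and 17/3/11% at 27% loss. The 27% is the fall from 44 to the 32 shown in Table 1, if that meant completers, which is not stated. At visit correlation 0.6 or 0.9, with 20% loss, it is 12/3/8% or 12/1/7%.

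**Step 2: late loss following the observed control-period change.** Simulated completer bias in the control-period change is +0.06/+0.11/+0.17 SD. The two changes share the Post-CTRL noise, so their covariance is 0.15² − 0.2 = −0.1775 and the regression slope is −0.1775/0.4225 = −0.42. The hydrotherapy-period bias is therefore −0.42 times the control-period bias (−0.03/−0.05/−0.07), and the difference is −1.42 times it (−0.09/−0.16/−0.24). Maximum likelihood gives about 0.00 throughout. Across the three log-odds, the difference runs from −0.05 to −0.13 at 10% loss and from −0.12 to −0.32 at 27%.

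**Step 3: false positives of the visit comparison at 5%, nothing changing at any visit, 20% late loss.**

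| Loss follows | RM-ANOVA | Mixed | Friedman's | Skillings-Mack |
|---|---|---|---|---|
| Chance | about 5% | about 5% | about 5% | about 5% |
| Observed control change | 7/12/26% | 5/5/5% | 7/11/19% | 5/5/6% |
| Unseen hydrotherapy-period change | 7/14/26% | 6/12/23% | 7/12/19% | 6/10/16% |

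Repeat runs put the RM-ANOVA figure of 26% for loss on observed control change at 24 to 26%.

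**Step 4: bias in the difference under other mechanisms (SD).**

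| 20% loss follows | Completers | Mixed model |
|---|---|---|
| Post-CTRL level | −0.04/−0.07/−0.10 | 0.00 |
| Constant individual slope | 0.00 | +0.02/+0.04/+0.06 |
| Unseen hydrotherapy-period change | +0.09/+0.16/+0.24 | +0.05/+0.09/+0.14 |
| Unseen control-period change (loss before Post-CTRL) | −0.09/−0.16/−0.24 | −0.08/−0.15/−0.23 |

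For 20% random loss before Post-CTRL, the precision gain is only 1%, 0% and 0.3% (control, hydrotherapy, difference). If 20% miss Post-CTRL alone, it is 3%, 3% and 0.4%.

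**The case against.** **This belongs in the analysis plan.** The protocol does not say completers only, and an SAP that is not shown may set missing-data rules. This stands as a limit on weight. But the two tests are stated choices, and a later rule would have to work around them.

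**The opening sentence on all participants is no promise to use all data.** This is correct. In context it explains why active and passive participants are not compared as groups, and no contradiction is claimed.

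**The false-positive figures assume nothing changes, while the protocol expects decline.** This is fair. With the assumed 0.2 SD decline per period and complete data, the three-visit test rejects about 93% of the time. For completers' Post-CTRL versus Post-hydrotherapy alone, with nothing changing and late loss on observed control change, two-sided rejection is about 6/8/10%, and false declarations of benefit fall to about 1%. The error runs against hydrotherapy.

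**The strongest mechanism is extreme.** Log-odds of 2 means about 86% loss for a boy 2 SD below the mean change and about 1% for one 1 SD above it. Loss on the Post-CTRL level gives RM-ANOVA false positives of only about 5 to 7%. The upper ends above should be read accordingly.

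**The largest biases concern a difference of changes that Data Analysis does not name.** True, but Research Objective judges results by exactly that comparison.

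**The remedy has limits.** It does little for early loss and is slightly worse under slope-driven loss. Skillings-Mack needs at least two visits and has no general guarantee under missing-at-random. These points stand and limit the claim, but they do not overturn it.

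**Conclusion.** The point holds as a modest, inexpensive improvement to a stated method. That the named tests discard partial records in standard form needs no assumption; every magnitude does, because the protocol gives neither a drop-out rate nor a within-person correlation.

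Under random late loss, the cost is precision, mostly in the control-period change and little in Post-CTRL versus Post-hydrotherapy. If late loss follows observed control-period decline, completers are biased against hydrotherapy and the visit tests reject too often; the mixed model avoids both. If loss follows unseen deterioration during hydrotherapy, both methods favour hydrotherapy and the mixed model only reduces the bias. Neither method removes the confounding of treatment with time in this fixed-order, single-arm design.

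**What to change.** In Data Analysis:

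- **Approximately continuous outcomes:** replace repeated-measures ANOVA with a linear mixed model with visit as a fixed factor, unstructured covariance, small-sample degrees of freedom (e.g. Kenward-Roger), and every participant with at least one visit. Report the control-period change, the hydrotherapy-period change and their difference.
- **Clearly non-normal or ordinal outcomes:** use Skillings-Mack in place of Friedman's for the visit comparison, and the mixed model with bootstrap intervals for the changes. A signed-rank test on each participant's difference of changes would again need all three visits.
- **Sensitivity analyses:** keep the completer analysis. Add one that shifts missing Post-hydrotherapy values over a pre-stated range in both directions and reports where the conclusion changes.
- **Data collection:** record whether each loss came before or after Post-CTRL.

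The cost is protocol wording, standard software and slightly more analysis work, with no added visits or participants. The price is reliance on missing-at-random. With skewed (exponential) noise, bootstrap intervals covered 91–94% rather than 95% and bias in the difference reached +0.06 SD. In the same check, completers' t-intervals for the control-period change covered 95/82/57% at log-odds 0/1/2.

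### The choice between repeated measures ANOVA and Friedman's test is tied to whether outcomes are parametric, but in this own-control design the assumptions to check are those of within-person changes

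*Protocol*

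**What the plan says.** Under Data Analysis, the three assessments ("Pre-CTRL vs Post-CTRL vs Post hydrotherapy") are compared "using repeated measures Anova (where outcomes are parametric) or Friedman's (where parametric assumptions are violated"). The section does not say whether this is judged on visit scores, on changes or on residuals. It does say that comparisons between ability groups are not the aim: "it is of interest if there is a change within the individuals themselves". The protocol design justification gives the matching design statement, that "the participants will act as their own controls".

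Under Participants and power calculation, the calculated n = 8 is raised to 44. Besides dropout and the novelty of the intervention, one reason given (item b) is the need to "fulfil the criteria for parametricity in a clinical condition that has a wide variance". The section explains that variance as follows: "children and adults with DMD ranging from 6-25 yrs are very varied in the presentation of physical function".

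Under Research Objective, the possible results are listed separately: improvement, a slower decline than in the control period, decline at an unchanged rate, and worsening.

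**The concern.** The two statements together direct the analyst to the wrong object. The first names the outcomes as the thing that is or is not parametric. The second identifies spread between participants as what endangers parametricity. In a comparison of each participant with himself, differences in level between a young ambulant boy and an older non-ambulant man drop out of the test. They say nothing about whether the ANOVA assumptions hold.

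Two things are at stake. An analyst who checks raw scores may abandon the mean-based analysis when the changes are well behaved, and lose power. And once an outcome goes to a within-person rank test, the size of change is gone, although the objectives turn on size of change.

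**Working it through.** **The plan's own figure.** The point neither disputes nor depends on n = 8. For reference, a two-sided paired t-test at alpha 0.05 with a standardised effect of 2 needs n = 6 for power 0.95 (power 0.971) and has power 0.998 at n = 8.

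**Step 1: between-person spread cancels.** Write the score of participant i at visit j as Y_ij = m_j + b_i + e_ij, with b_i his own level.
- A change is Y_i3 − Y_i2 = (m_3 − m_2) + (e_i3 − e_i2). The term b_i has gone.
- The ANOVA error term uses Y_ij − (person mean) − (visit mean) + (grand mean). Again b_i drops out.
- Friedman's test ranks within a person. Adding b_i to all three scores leaves the ranks unchanged.

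Simulation agrees (n = 44, 3 visits, alpha 0.05, 10,000 trials, normal within-person errors, assumed shift of 0.55 within-person SD at the third visit only). With between-person SD at 0, 1, 5 and 20 times the within-person SD, normal or lognormal, type I error was 0.044 to 0.053 for both tests. Power was 0.74 to 0.76 for ANOVA and 0.59 to 0.61 for Friedman's throughout.

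**Step 2: what a raw-score check would do.** In the same runs, a Shapiro-Wilk test on raw scores rejected normality in 41%, 98% and 100% of trials when the between-person spread was lognormal with SD ratio 1, 5 and 20. With normal spread it rejected in about 5%, however wide the spread. Shape triggers the switch; width alone does not.

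**Step 3: the cost of switching.** The table has n = 44, 4,000 trials per row and a shift of 0.6 within-person SD at the third visit. The protocol gives no within-person SD, so the shift and the error distributions are assumptions.

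| Between-person spread | Within-person errors | Raw scores flagged | ANOVA power | Power after raw-score rule |
|---|---|---|---|---|
| Two groups centred at 5 and 25, SD 3 | Normal, SD 1 | 100% (changes: about 5%) | 0.81–0.83 | 0.67–0.69 |
| Normal, SD 5.9 (the DMD QoL figure in the protocol) | Normal, SD 2 | 12% (any of 3 visits) | 0.82 | 0.80–0.81 |
| Two groups, as in row 1 | t with 3 df | 100% | 0.85–0.86 | 0.92 |

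Row 1 is a needless loss of about 14 points. Row 2 loses 1 to 2 points. In row 3 the switch gains 6 to 7 points. The 0.55-shift runs agree on reversal: ANOVA 0.79 against Friedman's 0.87 with t(3) errors, 0.79 against 0.999 with lognormal errors, and 0.78 against 0.99 when the within-person SD differs between people.

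**Step 4: size of change.** Take a score on which lower is worse. One participant loses 4 points and then 4 (unchanged rate); another loses 4 and then 1 (slowed). Both have within-person ranks 3, 2, 1. If all 44 decline at each step, the rank sums are 132, 88 and 44 whatever the rates, and

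Q = 12/(44 × 3 × 4) × (132² + 88² + 44²) − 3 × 44 × 4 = 616 − 528 = 88

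for slowed, unchanged and faster decline alike. A mean-based within-person analysis can test the contrast (visit 3 − visit 2) − (visit 2 − visit 1), which is −1 − (−4) = 3 in the slowed case and 0 in the unchanged case.

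**The case against.** The strongest case for the protocol has five parts.

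- **The wording can be read correctly.** The assumptions of a repeated measures ANOVA are about residuals and sphericity, so a violation of parametric assumptions may mean just that. The method of checking may stand in a SAP. This stands, and the loss is therefore conditional. It does not remove the point, because the protocol's own explanation of parametricity is spread between participants.
- **The wide-variance remark justifies the sample size and is not the trigger for Friedman's.** This stands. A reader might infer that the plan necessarily sends outcomes to a weaker test because participants differ widely. The text contains no such chain, and Step 2 shows that wide but normal spread does not cause the switch.
- **Friedman's is not generally weaker.** This stands. Its asymptotic relative efficiency of (3/π) × 3/4 = 0.716 for three visits tempts one to say that 44/0.716, about 61 participants, would be needed. That holds only for normal within-person errors. The protocol gives no data on these errors, and its design justification stresses how much the speed of decline differs between patients.
- **Error rates are not harmed.** This stands. In null runs the two-stage rule stayed close to 5%, so choosing the test by a pre-stated rule is not shown to inflate type I error.
- **A larger sample does help.** This stands in part. Tests of means are more robust to non-normality at 44 than at 8. But more participants do not make scores normal, and this robustness is a reason to keep the mean-based analysis.

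**Conclusion.** The point holds as one of wording with a conditional cost. The protocol attaches the choice of test to the outcomes, and parametricity to between-person spread, whereas its own-control comparison depends on within-person changes or residuals and on sphericity. The cost is about 14 points of power at n = 44 if three things coincide: the check is made on raw scores, those scores are two-humped or strongly skewed between people, and within-person errors are normal with a shift of 0.6 SD. With normal between-person spread the cost is 1 to 2 points. With heavy-tailed errors the switch gains power.

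The loss of size of change does not depend on those error assumptions. Where decline is monotone within participants, Friedman's statistic is identical for slowed and unchanged decline, which the objectives want told apart. The omnibus ANOVA F does not separate them by itself either, but its model supplies the contrast that does.

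Nothing here shows that the trial would be invalid or that 44 is the wrong number; dropout and novelty are also given as grounds for it.

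**What to change.** 1. **Data Analysis:** state that assumptions are judged on within-person changes or model residuals (with sphericity), and not on visit scores.
2. **Data Analysis:** make a within-person analysis that estimates the mean change with a confidence interval the pre-stated default for each outcome, for example repeated measures ANOVA or a mixed model. Include the contrast between the change over hydrotherapy and the change over the control period. Keep Friedman's as a sensitivity analysis.
3. **Participants and power calculation:** reword reason (b) so that spread between participants is not presented as a threat to parametricity. It can say that a larger sample makes mean-based tests more robust to non-normal changes.

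A sign-flip permutation test should not be adopted as the automatic substitute for skewed changes. It assumes symmetry under the null, and with mean-zero lognormal changes at n = 44 it rejected about 10.7% at a nominal 5%.

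The cost is a few sentences and a little analysis code. No extra data or participants are needed.
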